Study Protocol

Effects of Sleep hygiene Education on Sleep Health in Adults Ages 50 -80

[name]

Updated: 09/02/2024

NCT: 06129045

Approved by human subject protection review board committee on 09/02/2024

Experimental design: The two-year randomized control trial will begin in the fall (September 2023) and conclude before the end of the academic year (May 2025). The principal investigator and student researcher(s) will recruit participants through flyers and word of mouth. Flyers will be placed at senior centers, community centers, and medical centers in Rapid City, SD. Interested participants will email or call [name] to enroll in the study. [name] will meet with the participant to determine the eligibility status for the study. Due to the use of human subjects in this study, the research protocol will be approved by the University of South Dakota, Black Hills State University institutional review boards, and the National Institutes of Health before participant recruitment. Participant inclusion criteria will include participants ages 50-80, who own a smartphone with the capability of receiving text messages. Exclusion criteria: an untreated diagnosed sleep disorder such as insomnia or obstructive sleep apnea, and inability to wear any sleep tracking device on their wrist. During the initial visit, participants will read through and sign informed consent explaining the procedures and expectations of them during the study. The participants will then complete the following questionnaires related to the primary objectives of the study: the Ru-SATED questionnaire which includes the Sleep Diary (based on the Consensus Sleep Diary) and Epworth Sleepiness Scale, Pittsburgh Sleep Quality Index, and the Sleep Hygiene Index. Participants will also complete the Perceived Stress Scale, and the Numeric Pain Rating Scale as secondary outcomes. Initial data collection will consist of taking anthropometric measurements and vital signs, with the assistance of the student researcher. The anthropometric measurements will include the following: body weight, height, and body mass index (BMI). BMI will be calculated by the standard method (body weight [kg]/ height [m]2) from weight and height measurements. The vital signs assessed will be resting blood pressure, heart rate, and respiratory rate. Following anthropometric data collection and vital signs, the participants will be instructed on the use of the wearable sleep tracker and assisted with setting up and charging the device. Participants will be instructed to contact the PI with any questions throughout the study by email or phone.

A total of 120 participants will be recruited with 40 participants per group. The 40 participants per group are based on recently performed studies related to text messaging and sleep health. Participants will be randomly assigned to one of three groups. The three groups will consist of a control group in which no intervention will be performed, a one-time educational group that will watch a sleep hygiene video on behavior changes related to healthy sleep, and the third group will get the one-time educational video plus daily automated text messages reinforcing education learned in the video.

Following the initial meeting with the PI, all participants will wear the sleep tracker on their wrist for 2 weeks to collect preliminary data and then 4 additional weeks following their intervention for a total of 6 weeks. The sleep tracker will monitor the physiological markers of sleep provided by wearable technology on sleep efficiency, time in bed, time actually sleeping, sleep midpoint, and time spent at each stage of sleep. At the end of the 6-week study period, the PI and/or student researcher(s) will again meet with each participant. The participant will again complete the following questionnaires: Sleep diary, Epworth Sleepiness Scale, Pittsburgh Sleep Quality Index, Sleep Hygiene Index, Perceived Stress Scale, and Numeric Pain Rating Scale. Anthropometric data collection and vital signs will be reassessed. Pre/post measurements will be compared and data analyses will be conducted using a 2x2 mixed factorial repeated measures ANOVA test.

Assessing overall sleep health is relatively new and therefore there is no established gold standard, however the Ru-SATED questionnaire (Table 1) has been shown to be a reliable and valid measure of sleep health(26). We will use this in combination of objective data from the FitBit device to measure sleep health. Each sleep health domain will be dichotomized using the cut-off points in Table 1 with 0 = poor sleep health and 1 = good sleep health. The domains will be summed to create the composite sleep health score ranging from 0 - 6 with a higher score indicating better sleep health.

Table 1 Sleep Health Composite			
Sleep health domain	Source	Operational definition	Cut-off for good sleep health
Regularity	FitBit	Standard deviation of sleep midpoint, which is calculated as [sleep onset + (wake time – sleep onset/2)]	<60 min
Satisfaction	Sleep Diary	The sleep diary includes an item to rate “restedness upon awakening” with 0 = “not at all”, 1 = “somewhat”, 2 = “moderately”, 3 = “quite a bit”, and 4 = “extremely”. Satisfaction will be operationalized as the average “restedness” score	Average of ≥ 3
Alertness	Epworth Sleepiness Scale	Epworth Sleepiness Scale which consists of 8-items of various activities (ie. sitting and reading, watching TV, etc) answered using a 4-point Likert Scale with 0 = “would never nod off” to 3 = “high chance of nodding off”	≤ 10
Timing	FitBit	Average sleep midpoint	2am-4am
Efficiency	FitBit	Average total minutes of sleep divided by time in bed multiplied by 100	>85%
Duration	FitBit	Average total minutes of sleep	6-8 hours

Table 1: Sleep Health Composite

[figure not shown]

Figure 1: Study design for Specific Aim 1.

Specific Aim 2: Assess the ability of daily automated text messaging in CDOA to serve as an effective augmentation for sleep hygiene education. Several research studies have shown that a one-time sleep hygiene education session have improved sleep health in younger adults and working individuals(4, 27). With the promising results of a one-time education on short term progress, we want to test if longer-term reminders outside the initial training would provide even more sustainable results. The expansion of smartphone technology opens up an opportunity to reinforce the initial education with continual reminders of good sleep habits. A recent survey demonstrated that 86% of Americans over 50 utilize text messaging(28). In addition, one study showed text messaging significantly improved exercise rates in older adults(25). For this reason, we want to explore using automated text messaging for sleep hygiene education. *We hypothesize that automated text messaging will enhance the treatment effect of a one-time educational session on sleep health in CDOA.*

Experimental design: Following anthropometric data collection and vital signs, the participants will be randomly assigned to one of three groups (Figure 2). The third group, a one-time education plus automated text messaging, will receive daily automated text messages scheduled for 8:00 pm every evening. The text messages will include a variety of sleep hygiene behavioral tips for the participant to try (Table 2). The participants will receive the text messages for a total of 4 weeks. The control group and the one-time educational group will not receive any intervention during this time frame. Following the 4 weeks, PI and student researcher(s) will meet again with all participants to collect the same data that was collected at the initial visit. Each participant will have a total of 2 sessions to complete with each session taking approximately 45-60 minutes to complete.

[figure not shown]

Figure 2: Study design for Specific Aim 2.

Day	Daily Text
1 & 16	Go to sleep and wake up at the same time every day. This will help set your natural biological clock.
2 & 17	Exposure to bright natural light when you first wake up is also helpful to set your natural biological clock.
3 & 18	Use your bed for only sleep and sexual activity to help train your brain that if you are in your bed, you should be sleeping. Do not eat, work, or watch TV in bed. Do these activities outside of the bedroom.
4 & 19	Leave bed if unable to fall asleep within 20 minutes and return when sleepy. If unable to leave the bed due to limited mobility or safety concerns, do something relaxing (ie, relaxation techniques) until sleepy and able to fall to sleep.

5 & 20	Develop a relaxing bedtime routine. This may include taking a warm bath, reading a book, meditation, or stretching. Avoid stimulating activities right before bedtime, including watching TV or discussing a stressful topic.
6 & 21	Avoid moderate to vigorous exercise at least 2-3 hours before bedtime. Exercising immediately before bedtime stimulates your body and brain, making it hard to fall asleep. There is evidence however that doing regular (preferably moderate to vigorous) exercise improves your sleep at night. Talk to your physical therapist about an appropriate exercise program.
7 & 22	Avoid caffeinated foods and drinks at least 4 hours before bedtime (includes most tea, coffee, chocolate, and soft drinks). Check the presence of caffeine in your drink or food by reading the label. Caffeine can cause difficulty falling asleep and increase the number of times you wake up during the night.
8 & 23	Refrain from drinking alcohol or smoking at least 3 to 4 hours before bedtime. Although people may think drinking alcohol causes relaxation before bedtime it can actually increase the number of times you wake up during the night and can cause you to wake up early. Nicotine in cigarettes acts as a stimulant that can cause difficulty falling asleep.
9 & 24	Do not take unprescribed or over-the-counter sleeping pills.
10 & 25	Avoid daytime napping so that you are tired at night and can fall asleep easily. If you feel you need to take a nap, limit the nap to 30 minutes and avoid napping in the evening.
11 & 26	Make your sleeping environment comfortable and relaxing. This includes avoiding too much light and disturbing noises. Stop using light emitting electronics (ie, television, computer, smartphone) at least 30 minutes before bedtime as the blue light that is emitted can disrupt sleep by suppressing melatonin production. Use ear plugs, light-blocking curtains, or an eye mask if needed.
12 & 27	Keep the temperature comfortable. Being too warm or cold may disturb your sleep. Also, use a comfortable and supportive pillow and mattress.
13 & 28	Avoid eating a large meal or spicy food 2-3 hours before going to bed. Your digestive system slows down while you are sleeping, which can stimulate acid secretions that cause heartburn. A light snack may be helpful if you are hungry. Avoid excessive liquid 2-3 hours before bedtime.
14 & 29	Eat nutritious, well balanced meals. Avoid eating a large amount of highly processed and sugary foods as these can disrupt the hormones that help regulate your sleep patterns. Instead try to make a habit of eating whole foods whenever possible.
15 & 30	Talk to your doctor or health professional if you still have trouble sleeping.

Table 2: Sleep hygiene tips that will be sent out through text messaging

Health Relevance: The main goal of this project is to develop an understanding of effective sleep hygiene education methods in CDOA and their possible effect on sleep health. A long-term goal is to create an easy sleep hygiene education system that can be implemented by all healthcare practitioners to improve sleep health, which potentially could reduce the risk of developing chronic disease.

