## Data Analysis

Statistical analyses will begin with the collection and reporting of demographic information for all study participants. This information will provide context for the sample and allow for appropriate interpretation of study outcomes.

Pre- and post-intervention survey data will be analyzed using paired-sample t tests. This approach will compare participant scores from the surveys administered at the beginning of the study to scores from the same surveys administered at the conclusion of the study, allowing for assessment of within-subject changes over time.

In addition to survey measures, objective sleep tracker data will be analyzed using paired-sample t tests. This will allow for comparison of baseline sleep measures with post-intervention measures, providing an additional source of quantitative evidence regarding the impact of the intervention.

All statistical analyses will be conducted using appropriate statistical software, and significance will be set at  $p < .05$ .

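### The only between-arm analysis named is a pre/post ANOVA that compares change scores, and the SAP has none; one baseline-adjusted model would supply both contrasts, usually with better precision

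*Protocol*

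**What the plan says.** The Protocol (Experimental design) describes three arms: "Participants will be randomly assigned to one of three groups", and "A total of 120 participants will be recruited with 40 participants per group". The arms are a control, a one-time video, and the video plus daily texts. Its analysis sentence reads: "Pre/post measurements will be compared and data analyses will be conducted using a 2x2 mixed factorial repeated measures ANOVA test". The design is written as 2x2 although there are three arms, and neither the term to be tested nor any baseline covariate is named.

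The SAP (Data Analysis) describes something else. For questionnaires: "Pre- and post-intervention survey data will be analyzed using paired-sample t tests". For the tracker: "objective sleep tracker data will be analyzed using paired-sample t tests". It gives the purpose of the survey tests as "allowing for assessment of within-subject changes over time". It contains no comparison between arms.

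Baseline values are planned for every outcome. Questionnaires are completed at the first visit and again at the end, and the tracker is worn for two weeks before the four intervention weeks. Under Specific Aim 2, the Protocol places random assignment after the anthropometric and vital-sign measurements, which belong to the first visit.

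**The concern.** The aims concern differences between arms. Aim 2 in particular asks what texting adds to the video, an increment between two active arms of 40, so precision is likely to be the limiting factor. A change-score comparison subtracts the whole baseline value whatever its actual relation to the outcome. When the true slope is below 1, this over-corrects chance baseline differences and adds noise. The data needed to do better are already being collected.

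The SAP's paired tests cannot take the ANOVA's place. A pre/post change within an arm mixes the intervention with time, repeat testing and regression to the mean, and does not use the control arm.

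**Working it through.** **Inputs.** From the documents: three arms, 40 per arm, two time points, and the 0.05 level ("significance will be set at" p < .05; taken as two-sided, since the sidedness is not stated). Assumed: the pre/post correlation r and the pre and post SDs, s0 and s1.

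**The plan's own figure.** The stated basis for the sample size is: "The 40 participants per group are based on recently performed studies related to text messaging and sleep health". No effect size, SD or power is given, so 40 per arm can be neither reproduced nor refuted.

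**Step 1: what the ANOVA tests.** With two time points, the arm-by-time F equals the F from a one-way ANOVA of post minus pre. In a simulated 3 x 40 data set both came to 2.4159.

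**Step 2: residual variance per person.**
- Change score: s0² + s1² − 2·r·s0·s1
- Baseline-adjusted: s1²·(1 − r²)
- Saving, the first minus the second: (s0 − r·s1)², which is never negative and is zero when r = s0/s1

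With s0 = s1 = 1 these become 2(1 − r) and 1 − r², and their ratio is (1 + r)/2.

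**Step 3: equal SDs, 40 against 40.** Power is for a 0.5 SD difference, from the two-sample noncentral t with 78 degrees of freedom, before the small slope cost in Step 4.

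| r | Change variance | Adjusted variance | Reduction | Power, change | Power, adjusted |
|---|---|---|---|---|---|
| 0.3 | 1.40 | 0.91 | 35% | 46% | 64% |
| 0.5 | 1.00 | 0.75 | 25% | 60% | 72% |
| 0.8 | 0.40 | 0.36 | 10% | 94% | 96% |

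At r = 0.5 the difference detectable with 80% power falls from 0.634 to 0.634 × √0.75 = 0.549 SD. The precision is that of 40/0.75 = 53 people per arm analysed by change scores. At r = 0.9 the reduction is only 5%.

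**Step 4: price of estimating the slope.** The variance is multiplied by 1 + 1/(120 − 3 − 2) = 1.0087, or about 0.9%. The net reductions are 34.4%, 24.3% and 9.2% at r = 0.3, 0.5 and 0.8. Simulation of 20,000 trials of 3 x 40 at each r gave 33.4%, 23.9% and 9.7%. Both estimators were unbiased.

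**Step 5: unequal SDs (s0 = 1).**
- s1 = 1.2, r = 0.8: change 0.5200, adjusted 0.5184, saving (1 − 0.96)² = 0.0016, or 0.3%. After the slope cost, 0.5184 × 1.0087 = 0.5229, a very small net loss.
- s1 = 0.8, r = 0.3: change 1.160, adjusted 0.582, saving 0.578, or about 50%.

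**The case against.** The strongest reply is that this is a choice of efficiency. In a randomised trial the change-score contrast is valid and unbiased, and it does use the baseline, with a slope of 1. If r is high the gain is slight: power goes from 94% to 96% at r = 0.8. The mismatch between the two documents, and the 2x2 label for three arms, are more basic problems. All of this stands, and it limits how strongly the point can be put.

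A second reply is that the tracker baseline may not be a clean covariate. The Protocol places assignment at the first visit and the tracker weeks follow it. When participants learn their arm is not stated. If they learn it then, the baseline for every tracker measure, and for four of the six composite domains (regularity, timing, efficiency, duration), could be affected by that knowledge. This also stands, but it counts equally against the change score, which subtracts the same baseline.

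Four stronger readings should be resisted:
- That the variance reduction is a known figure. The documents give no correlation or SD.
- That adjustment wins for every r below 1. That needs equal SDs; Step 5 shows a near-zero case.
- That the SAP repeats the ANOVA problem. Its paired tests have no between-arm term for a covariate to sharpen.
- That the ANOVA's group main effect would be read as the treatment test. It averages pre and post and so halves the effect; power for 0.5 SD at r = 0.5 would be about 25%. The tested term is unnamed, but the sentence speaks of comparing pre with post, and nothing points to the main effect.

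**Conclusion.** The point holds as a recommended improvement in precision and clarity; it is not a failure of validity. The only between-arm analysis in the documents is a change-score comparison, no baseline covariate is planned, and the SAP does not carry a between-arm analysis at all. Under equal SDs and r between 0.3 and 0.8, baseline adjustment lowers the contrast variance by about 35% to 10%. Outside those assumptions the gain runs from about nothing to about one half in the cases examined. The largest loss that adjustment can bring is the slope cost of about 0.9% of variance at N = 120. The gain can be realised only once a between-arm analysis is restored to the SAP.

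**What to change.** Reconcile the two documents by replacing both the Protocol's ANOVA sentence and the SAP's paired tests, before outcomes are examined by arm. For the composite, each tracker measure and each questionnaire score, fit one linear model of the post value on arm (three levels) and the participant's own baseline value of that outcome. Report video minus control, and video plus text minus video, as adjusted mean differences with 95% confidence intervals. Pre/post changes within arms can remain as description. Individual dichotomised domains, if analysed separately, need a model for binary data.

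State when each participant learns the arm, and confirm that this is after the two-week tracker baseline is complete. If that cannot be confirmed, adjust the tracker outcomes and the composite only for baseline data collected before disclosure, such as the first-visit questionnaire scores.

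The cost is a rewritten SAP analysis section, because adding a covariate to paired tests is not enough, and one residual degree of freedom per outcome. No new data are needed.

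### The protocol states a 2x2 mixed ANOVA for a trial with three arms and two time points; no single 2x2 model holds all three arms, and the visible text does not name the arms to be compared

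*Protocol*

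**What the plan says.** The protocol's opening Experimental design section sets out the allocation: "Participants will be randomly assigned to one of three groups". The arms are a control with no intervention, a one-time video, and a combined arm: "the third group will get the one-time educational video plus daily automated text messages reinforcing education learned in the video". On size it says "A total of 120 participants will be recruited with 40 participants per group". The Experimental design text under Specific Aim 2 repeats the three-group randomisation and fixes the number of assessments: "Each participant will have a total of 2 sessions to complete".

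After describing the pre and post measurements, the opening section gives the analysis: "data analyses will be conducted using a 2x2 mixed factorial repeated measures ANOVA test". The protocol text names no other between-group test.

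The Specific Aim 2 hypothesis is that "automated text messaging will enhance the treatment effect of a one-time educational session on sleep health in CDOA". That is a comparison of video plus texts with video alone.

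The SAP's Data Analysis section lists paired t tests for the surveys and for the tracker data, with significance at p < .05. Neither test has a group factor.

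**The concern.** A 2x2 mixed ANOVA has one between-subject factor with two levels and one within-subject factor with two levels. Time (pre, post) fills the second, which leaves two levels for three randomised groups. The model named does not fit the design described a few sentences earlier in the same section.

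The way three arms are reduced to two decides which question is answered:

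- Merging the two education arms removes the texting comparison, which is the Aim 2 hypothesis.
- Leaving out the video-only arm compares video plus texts with control, so the effect of the texts cannot be separated from that of the video.
- Leaving out the control leaves the one-time education untested against no intervention.

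As long as the pairing is unnamed, it can be chosen after the data are seen.

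**Working it through.** **Inputs.** Groups g = 3, with 40 per group and N = 120 (protocol, opening Experimental design). Times t = 2 (protocol, Specific Aim 2, Experimental design). Stated model: 2x2. Alpha: 0.05 (SAP, Data Analysis). The sample size is internally consistent: 3 x 40 = 120.

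**Trying to reproduce the stated layout.** Cells = g x t = 3 x 2 = 6. The stated model has 2 x 2 = 4, so 2x2 is not reproduced. For the group-by-time interaction, df = (g - 1)(t - 1) and error df = (N - g)(t - 1).

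| Model | Participants | Interaction test |
|---|---|---|
| 3x2, all arms | 120 | F(2, 117) |
| 2x2, one arm left out | 80 | F(1, 78) |
| 2x2, two arms merged | 120 | F(1, 118) |

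Leaving out one arm sets aside 40/120 = 33% of participants in that model.

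**What each 2x2 estimates.** Let d1 be the effect of the video on mean change and d2 the added effect of the texts. Relative to control, the arms change by 0, d1 and d1 + d2.

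- Video v control: d1.
- Video plus texts v video: d2.
- Video plus texts v control: d1 + d2.
- Merged education arms v control: [d1 + (d1 + d2)]/2 = d1 + d2/2. No term isolates d2.

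Reading 2x2 as education (yes/no) by texts (yes/no) also fails. It would need a texts-only arm, which does not exist, and it leaves no place for time.

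**Illustration of the stakes.** With two times, the interaction test is equivalent to comparing change scores between groups. The documents give no effect size or SD; the sample size rests only on this: "The 40 participants per group are based on recently performed studies related to text messaging and sleep health". So assume a change-score SD of 1 and two-sided 0.05. For a two-group contrast the noncentrality is difference/sqrt(1/n1 + 1/n2).

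- True changes 0 / 0 / 0.5. The merged contrast is (0 + 0.5)/2 = 0.25, with noncentrality 0.25/sqrt(1/40 + 1/80) = 1.29 and power 25%. The direct contrast of video plus texts with video has noncentrality 0.5/sqrt(2/40) = 2.24 and power 60%. The 3x2 interaction F(2, 117) has power 62%.
- True changes 0 / 0.5 / 0.5. The merged contrast is 0.5, with noncentrality 0.5/sqrt(1/40 + 1/80) = 2.58 and power 73%; the 3x2 F has 62%.

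Merging can therefore lose or gain power, depending on the pattern. Under neither pattern does it test d2.

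**Separate two-arm 2x2s.** Each uses 80 people, but control v video and video v video plus texts together use all 120. With each tested at 0.05 without adjustment, the chance of at least one false positive would be 1 - 0.95^2 = 9.75% for two independent tests and 1 - 0.95^3 = 14.3% for three. The pairs share arms, so the tests are correlated. Simulation of 200,000 null trials (normal change scores, equal variances) gives about 9.1% for these two pairs and 12.2% for all three.

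**The case against.** The strongest reply is that one 2x2 per aim was meant. The sentence speaks of analyses in the plural and comes before Figure 1, which belongs to Specific Aim 1. Specific Aim 2 has its own design text and Figure 2. Control v video for the first aim and video v video plus texts for the second would use every arm and answer both questions. This is plausible, but the opening section introduces all three groups before it states the model, and nothing in the visible text assigns pairs to aims. Even on this reading, the pairs and the handling of two tests have to be written down.

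A second reply is that 2x2 is a slip for 3x2. That may be so, and then none of the harms above would arise. It would still leave the protocol's only stated between-group model wrong.

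A third reply is that the SAP governs and uses paired t tests, so the 2x2 would never be run. This stands as a limit on the effect of the point: correcting the protocol alone would not change the results. It also means that restoring the protocol's ANOVA to repair the SAP would bring in a model that does not fit the design.

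The content of both figures and an earlier part of the SAP could not be seen. Figure 1 might show which groups the first aim compares.

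**Conclusion.** Wrong as written. The design is 3x2 (6 cells) and the stated model is 2x2 (4 cells). That rests on the protocol's own counts and on no assumption. Any single 2x2 either analyses 80 of 120 participants or merges two arms, and merging the education arms leaves Aim 2 without a test.

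A reader might infer that the trial must discard or pool an arm, or that a third of the sample will go unused. The documents do not support either. Both arise only if exactly one 2x2 model is run, and the 33% only if that model omits an arm. One 2x2 per aim would use everyone, and nothing in the text proposes pooling or dropping an arm. What is established is that the model does not match the design and that the visible text names no comparison.

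The power figures rest on an assumed SD and assumed effects and are illustrative only. The family-wise error figures assume unadjusted tests.

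**What to change.** In the protocol's analysis sentence, replace 2x2 with 3 (group: control, video, video + text) x 2 (time: pre, post), fitted to all randomised participants with available data. A conventional repeated-measures ANOVA drops anyone without a post value, so state how missing values are handled.

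Pre-specify two group-by-time contrasts: video minus control for the one-time education question, and video + text minus video for Specific Aim 2. State how multiplicity across the two is handled. Bonferroni, for example, would test each at 0.05/2 = 0.025; a different rule is acceptable if it is fixed in advance.

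Put the same model in the SAP's Data Analysis section, in place of the paired t tests, as the between-group analysis. If one two-arm model per aim is preferred, name each pair and give the multiplicity rule.

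The cost is a short edit to the protocol and replacement of the method text in the SAP. It needs no new data and no added participants.

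### Good sleepers are eligible, yet all six sleep health domains are scored 0/1, so the 0-6 composite cannot show gain in a domain already inside its cut-off and loses an unknown share of information

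*Protocol*

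**What the plan says.** Eligibility, in the protocol's first Experimental design section, is broad: "Participant inclusion criteria will include participants ages 50-80, who own a smartphone with the capability of receiving text messages". Nothing there requires poor sleep. The sleep-related exclusion is "an untreated diagnosed sleep disorder such as insomnia or obstructive sleep apnea", which removes some of the worst sleepers and none of the good ones.

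The scoring rule is "Each sleep health domain will be dichotomized using the cut-off points in Table 1", with 0 for poor and 1 for good, followed by "The domains will be summed to create the composite sleep health score ranging from 0 - 6". Table 1 gives the cut-offs:

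- Regularity: SD of the sleep midpoint under 60 minutes.
- Satisfaction: mean restedness of 3 or more on a 0-4 item.
- Alertness: Epworth total of 10 or less.
- Timing: defined as "Average sleep midpoint", good if between 2 am and 4 am.
- Efficiency: above 85%.
- Duration: 6 to 8 hours.

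Each underlying measure is continuous or multi-level. The Specific Aim 2 hypothesis is stated in terms of sleep health. The same Experimental design section also ties "Pittsburgh Sleep Quality Index, and the Sleep Hygiene Index" to the primary objectives and states no cut-off for either. The SAP's Data Analysis section plans paired t tests on survey scores and on tracker measures. It mentions neither the composite nor any dichotomy.

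**The concern.** In a sample not selected for poor sleep, many participants may start on the good side of several cut-offs. Within such a domain the 0/1 score has no room to rise. Outside it, real progress that stops short of the threshold is invisible, while a trivial change across the threshold earns a full point. If the Aim 2 conclusion rests on the 0-6 count, the trial would have less ability to separate the three groups than the collected data allow. With 40 per group there is little precision to spare, least of all for the contrast of video plus texts against video alone.

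**Working it through.** **The plan's own figure.** The protocol states "A total of 120 participants will be recruited with 40 participants per group" but gives no effect size, SD, power or dropout, so 40 per group can be neither reproduced nor refuted. Back-solving for two groups, two-sided alpha 0.05 (sidedness assumed) and 80% power: d = (1.960 + 0.842) × √(2/40) = 0.63. That is the detectable difference before any loss from cutting.

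**What the scoring does, from Table 1 alone.**

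| Change | Score before | Score after |
|---|---|---|
| Epworth 9 to 5 | 1 | 1 |
| Efficiency 78% to 84% | 0 | 0 |
| Midpoint SD 110 to 65 min | 0 | 0 |
| Efficiency 84.9% to 85.1% | 0 | 1 |
| Duration 7 h 50 min to 8 h 05 min | 1 | 0 |

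**One domain.** For a normal measure cut where a proportion p is already good, at normal quantile c, the efficiency kept is φ(c)² / [p(1 − p)]:

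- p = 0.5: 0.399² / 0.25 = 0.64
- p = 0.7: 0.348² / 0.21 = 0.58
- p = 0.8: 0.280² / 0.16 = 0.49
- p = 0.9: 0.175² / 0.09 = 0.34

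**The composite, by simulation.** All inputs are assumptions: six normal domains, one-sided cut-offs, the same p in each, pre/post correlation 0.6, between-domain correlation 0.2. Efficiency kept is the squared ratio of standardized effects, 0-6 count over uncut average, each adjusted for its own baseline. Figures carry simulation noise of a point or two.

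| Share already inside each cut-off | Everyone shifts 0.3 SD in every domain | Only out-of-range domains improve |
|---|---|---|
| 50% | about 65% | 71-76% |
| 70% | about 55% | 95-105% |
| 80% | about 46% | 78-145% |

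The ranges in the last column cover a 0.3 SD shift confined to those domains, and a larger shift scaled so that the mean stays at 0.3 SD. In the uniform case the loss is like having 40 × 0.46 = 18 to 40 × 0.65 = 26 informative participants per group instead of 40.

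**Sensitivity.** With unadjusted change scores and the same uniform shift, the composite kept 59%, 48%, 37% and 23% at 50%, 70%, 80% and 90% inside. Varying the correlations (pre/post 0.4-0.8, between-domain 0-0.4) widened this to 41-67%, 34-54%, 25-44% and 15-29%.

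**Full ceiling.** The share starting at 6/6 under these assumptions (between-domain correlation 0.2) would be about 6%, 20%, 35% and 59% at 50%, 70%, 80% and 90% inside.

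**Limits.** Timing and Duration have windows, not one-sided cut-offs. Movement inside a window is not clearly improvement, so less is lost in those two domains than the simulation implies.

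**The case against.** The strongest reply is that the uniform shift favours the concern. Good sleepers may have little to gain, and if benefit falls only where a domain is out of range, cutting costs little and can even help. That stands, and it is why the size cannot be fixed from the documents.

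A second reply is that the SAP already tests survey and tracker measures with no dichotomy mentioned, and that the Pittsburgh Sleep Quality Index and Sleep Hygiene Index carry no cut-off. This also stands. A reader might infer that the trial could report no effect although every underlying measure moved. The documents do not support that, because on its face the SAP would show movement in those measures. What the SAP does not provide is an uncut overall sleep health score compared between groups.

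A third reply is that the protocol cites Ru-SATED as reliable and valid, and clinical cut-offs are easy to read. But the protocol also says there is no gold standard, takes four of the six domains from the tracker, and gives no reason for the 0/1 cut. Validity does not establish responsiveness over four weeks. Interpretability is a good reason to keep the count, though not to rely on it alone.

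A reader might also infer that Timing is beyond the intervention's reach. Table 2 does not support this: its texts address fixed sleep and wake times (days 1 and 16) and morning light (days 2 and 17), either of which could move the midpoint.

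**Conclusion.** The concern holds in a limited form. Good sleepers can enrol, every domain is cut to 0/1, and a domain inside its cut-off cannot register improvement. Under a uniform 0.3 SD improvement with 50-80% already inside, the composite keeps about 46-65% of the efficiency of the uncut average. If only out-of-range domains improve, the loss ranges from modest to none.

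Two stronger readings are tempting. One is that most of the outcome's responsiveness is lost. That is not established: it depends on baseline pass rates that the documents do not give and on who improves. Even in the uniform case the standardized effect falls only to √0.46 = 68% up to √0.65 = 81% of its uncut size. The other is that anyone inside a cut-off cannot improve on the composite. The ceiling is per domain; a participant can still gain in other domains, and only 6/6 is a complete ceiling.

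This is a worthwhile improvement to the analysis, not an error that invalidates the design.

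**What to change.** Keep the 0-6 count and add a graded sleep health score, compared between groups with its baseline value as covariate:

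- Keep midpoint SD, mean restedness, Epworth total and efficiency % on their own scales.
- Score Timing and Duration as minutes outside the Table 1 window, with 0 inside it. This assumes no optimum within the window, and 8 h 05 min counts as 5 minutes out instead of a lost point. Distance from the window's centre would be unsuitable, since nothing in the documents makes 3 am or 7 hours a target.
- Orient all six so that higher is better, standardize each by its baseline SD, and average.

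Adjust the 0-6 count for its own baseline too, and report for each domain how many participants already scored 1 at baseline. State before outcomes are examined which of the two scores carries the Aim 2 conclusion.

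The cost is protocol and SAP wording and a little more analysis; no new data, visits or participants. The graded score is less intuitive than a count and less comparable with the cited composite, which is why the count stays. Timing and Duration still flatten inside their windows by design, so the gain may be smaller than the comparison with a fully uncut average suggests.
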